Trial Protocol

Title: "Longitudinal trial assessing cellulite in women wearing a new compression garment - one side with ink printed micro-pads ("Vari-pads") and one side without."

Principal Investigator: [name] MS FRCS(Gen) FCPhleb

Protocol Identifying Number: TWC-SM-2023-01

Protocol version number & date: v 1.1 28 June 2023

Ethics: Not required according to HRA Decision Tools (see Result - England Ethics 21-May-

2023) – and confirmed by e-mail from MHRA.

NCT: To be registered on ClinicalTrials.gov on confirmation of Ethics position

Background:

Cellulite is a very common condition that affects up to 90% of women.¹ It is much less commonly found in men. It presents as a dimpling principally of the skin of the buttocks and thighs, with the appearance having been described as resembling "orange peel", "cottage cheese" or a "quilt". In women who are affected, it usually appears after puberty. It occurs in all races, but is thought to occur more commonly in Caucasians.¹

The product being tested:

The product being tested is to be a retail (non-medical) product presented as standard compression shorts with a pattern of small, raised pads ("Vari-pads") of different heights printed on the inner aspect. A previous trial that we have performed has suggested that wearing these for eight hours a day can reduce the appearance of cellulite.² In addition, subjects found these compression pants to be very comfortable.²

In this trial, we want to see whether the subjective and objective improvement is due to the compression alone, or whether the Vari-pads on the inside of the product enhance the subjective or objective impression of cellulite. As such, we have asked the manufacturer to produce pairs of pants where the Vari-pads are printed onto the inner aspects as per usual on one side only, but not on the other side.

Subjects will then be asked to wear the apparel for at least eight hours a day, at times most suitable for themselves.

If and when they notice a difference between the appearance of cellulite between the two sides, they will notify us and we will then swap them into the 'normal' garments with Vari-pads on both sides, which they are then welcome to continue to wear.

Subjects:

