- 4] Variable end-point visit whenever the subject can tell that there is a difference between the left and right sides if the subject does not reach this end point, they will only have 3 visits and will not need the garment with Vari-pads on both sides.

First Visit (day zero):

Subjects will be asked to sign a consent form if they have asked sufficient questions and have decided to go ahead with the trial.

- Their cellulite will be graded as per the Nürnberger F, Müller grading system³

Grading	Description
Scale	
0	No alteration to the skin surface - NO CELLULITE SO THESE
	SUBJECTS will be EXCLUDED
1	Skin is smooth whilst subject is standing/lying, but alterations can be seen
	by pinching the skin, or by muscle contraction
2	'Orange-peel' or mattress appearance is evident upon standing without the
	use of any manipulation (pinching or muscle contraction)
3	Alterations seen in grade two presented together with raised areas and
	nodules

- Standard high-resolution photographs will be taken of their buttocks from behind, side and obliquely in the standing position with the muscles relaxed. The same will then be performed for the thighs. [Subjects will not be photographed in any way so as to be able to identify them.]
 - Subjects will have height and weight measured and noted.
- Localised transcutaneous water content measurement using LymphScanner (Delfin Technologies, Finland) this is a non-invasive device passed over the skin to determine the electrical conductance of the skin and sub-cutaneous tissues.
- They will be given a Celluqol[®] Quality of life questionnaire (long version see appendix)⁴ to complete.
- They will then be given the garment (x2) with one side covered with the Vari-pads, with the other side without any raised pads.

Variable End-point Visit:

When subjects can see or feel a significant difference in the cellulite of their buttocks and/or thighs between the sides, they will contact us and return for assessment.

At this visit, the following will be performed:

- Weight
- Photographs
- Questions as to the routine of garment wearing how many hours per 24 and when
- Transcutaneous water content buttocks and thighs
- Celluqol® QOL Questionnaire
- They will be given 2 new garments with Vari-pads on BOTH sides.

3 Months Visit.

At this visit, the following will be performed:

- Weight
- Photographs
- Questions as to the routine of garment wearing how many hours per 24 and when
- Transcutaneous water content buttocks and thighs

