- Cellugol® QOL Questionnaire

6 Months Visit - end of trial and £100 paid if all visits completed. The subject can keep the x2 bilaterally padded garments.

At this visit, the following will be performed:

- Weight
- Photographs
- Questions as to the routine of garment wearing how many hours per 24 and when
- Transcutaneous water content buttocks and thighs
- Celluqol® QOL Questionnaire

Primary endpoint:

- The time taken for patients to notice a self-determined significant difference between their right and left side and request the full garment.

Secondary endpoints:

- Quality of life changes by Celluqol® questionnaire 0, 3 and 6 months.
- Changes in photographs 0, 3, 6 months as assessed by 2 'blinded' observers
- Changes in transcutaneous water measurements

Interim Analysis:

We will perform an initial analysis when all of the results are in from the 1 month and 3 months visit.

Consent form: Please see attached.

Subject information sheet: Please see attached.

Insurance: The Whiteley Clinic has full insurance cover for clinical trials.

Payment: Subjects who complete the trial to 6 months will be allowed to keep the compression garments (worth £90.00 each) and will be given £100 in compensation for their time and travel.

References:

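### The primary event is stated with two conflicting thresholds, a difference or a significant difference, and with no direction, so event dates are ambiguous and a worse padded side counts as an event

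*Protocol*

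**What the plan says.** The event is described in four places in the Protocol.

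- **The product being tested:** "If and when they notice a difference between the appearance of cellulite between the two sides, they will notify us". The woman is then moved to the garment padded on both sides.
- **The Trial, visit list, item 4:** the extra visit takes place "whenever the subject can tell that there is a difference between the left and right sides". The same item treats this as the end point: "if the subject does not reach this end point, they will only have 3 visits".
- **Variable End-point Visit:** this section sets the trigger as follows: "When subjects can see or feel a significant difference in the cellulite of their buttocks and/or thighs between the sides, they will contact us". At that visit she receives two fully padded garments.
- **Primary endpoint:** "The time taken for patients to notice a self-determined significant difference between their right and left side and request the full garment".

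No sentence says which wording governs. No question or scale fixes what *significant* means beyond the woman's own judgement. Nothing says whether the event date is the day she notices, the day she contacts the site or asks for the garment, or the day of the visit.

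The procedures at the Variable End-point Visit are weight, photographs, wearing routine, water content, the quality-of-life questionnaire and the new garments. None of them records which side she judges better.

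**The concern.** For a self-reported time-to-event outcome, the instruction that tells a woman when to come forward is the measuring instrument. Here two sentences set it at a difference and two at a significant difference. Which sentence is followed can decide both when an event occurs and whether one occurs at all.

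The event also triggers an intervention, because the half-padded garment is replaced. A wrong trigger is therefore not just a coding problem to sort out at analysis: it ends the comparison in that woman.

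Separately, the stated aim is directional: do the pads improve the appearance of cellulite beyond compression alone? An event that only requires the sides to differ does not answer that.

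**Working it through.** No arithmetic applies. The protocol states no expected event rate, effect size, alpha or power for this endpoint, so there is no figure to reproduce. The check sets the four statements side by side.

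| Place | Threshold | Sense | Body site | Completing action |
|---|---|---|---|---|
| The product being tested | a difference | appearance | not stated | notifies the site, is swapped |
| Visit list, item 4 | a difference | not stated | not stated | none stated |
| Variable End-point Visit | significant difference | sight or touch | buttocks and/or thighs | contacts the site, returns |
| Primary endpoint | self-determined significant difference | not stated | not stated | requests the full garment |

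The first two rows share one threshold and the last two share another. Sense and completing action vary further within each pair.

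Five cases show the consequence. The week numbers are illustrative assumptions.

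1. *A slight visible difference at week 4 becomes significant at week 10.* The event is at week 4 under the first two rows, and at week 10 at the earliest under the last two. The event time moves by at least 10 − 4 = 6 weeks.
2. *A slight difference never becomes significant by 6 months.* She is an event under the first two rows and event-free under the last two.
3. *A significant difference in the cellulite is felt but not seen.* She is an event under Variable End-point Visit and not under The product being tested.
4. *A significant difference is noticed but the full garment is not requested.* She is an event under the visit list and not under Primary endpoint.
5. *The woman in case 1 is swapped at week 4 on the lower threshold.* From then on she wears pads on both sides. The significant difference that would have appeared at week 10 in the half-padded garment can no longer occur, so her time to the stated endpoint cannot be observed.

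Direction is checked in the same way. All four statements speak only of a difference between the sides, and none names the better one. A woman whose padded side looks significantly worse and who asks for the full garment meets the Primary endpoint as written. The event visit holds no item that would let the analyst separate her from a woman whose padded side looks better. The blinded reading of photographs does not fill the gap, because that secondary endpoint is set at 0, 3 and 6 months and is not the woman's own judgement.

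**The case against.** The best defence is that only one section carries the heading Primary endpoint, and that the dedicated visit section agrees with it on *significant*. The other two statements are a background description and a line in a schedule. The threshold is also self-determined, and three of the four statements depend on the woman coming forward, which narrows the practical gap. The information sheet, which is what women actually read, is attached to the protocol but not shown, and it may already use a single wording. All of this stands, but it does not remove the conflict. The schedule line itself calls the lower threshold the end point and uses it to decide who has no event, and the background text uses it to trigger the swap.

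A second defence is that a statistical analysis plan could choose the event date and classify events. It could do so for dates that were recorded. It could not restore a contrast already ended by a swap, or supply a side that was never recorded.

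A third is that direction is a separate matter and would remain if the wordings were identical. That is correct. It is included because it concerns the same definition and is mended by the same edit.

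Three stronger readings are tempting and not supported:

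- *A reader might infer four distinct definitions.* There are two thresholds. Asking for the garment is close to the notifying or contacting that leads to the swap elsewhere.
- *A reader might infer that the word feel lets in the sensation of raised pads on one side.* The sentence refers to a difference in the cellulite: "When subjects can see or feel a significant difference in the cellulite of their buttocks and/or thighs between the sides". It does not count the feel of the garment.
- *A reader might want a size in events or in median time.* Nothing in the protocol links either wording to an event rate, so any such figure would be invented.

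**Conclusion.** The point holds as an internal inconsistency in the primary event, together with a missing direction. For an individual woman the effect can be complete: an event under one wording and none under another. For the 60 women as a group its size cannot be derived from the document. The conclusion rests only on the protocol's text. It does not assume what the information sheet says or which wording staff would follow.

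The matter belongs in the protocol rather than in the analysis plan, because the swap made on the event cannot be reversed and because the side judged better must be collected at the visit.

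**What to change.** - Reconcile the four statements to one event definition with one threshold, one stated sense and one event date (noticing, request or visit). The choice of threshold is the sponsor's. If it departs from the significant difference now in the Primary endpoint section, the protocol should say so openly. In choosing the sense, bear in mind that grade 1 women are eligible and that their skin is smooth unless pinched or contracted, so an appearance-only event may be hard for them to register.
- Check that the information sheet carries the same definition.
- Add one item to the Variable End-point Visit: which side the woman judges better, read against which side of her garment was padded.
- Report events with the padded side better separately from events with the unpadded side better, so that only the former count as evidence for the pads.

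The cost is wording changes and one extra question. The downside is possibly fewer or later events than under the looser wording.

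### For women swapped to two-sided garments, the photograph endpoint omits their last one-sided photographs and reads later ones that have no current unpadded side

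*Protocol*

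**What the plan says.** The section on the product being tested asks whether improvement comes from compression alone or "whether the Vari-pads on the inside of the product enhance the subjective or objective impression of cellulite". The trial garments carry pads on one side only, so the comparison is within each woman.

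The same section sets the swap: when a woman notices a difference, "we will then swap them into the 'normal' garments with Vari-pads on both sides, which they are then welcome to continue to wear". The visit list places the variable visit "whenever the subject can tell that there is a difference between the left and right sides" and adds that "if the subject does not reach this end point, they will only have 3 visits". At the Variable End-point Visit, weight, photographs, wear questions, water content and Celluqol come first. The last item is "They will be given 2 new garments with Vari-pads on BOTH sides".

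The 3- and 6-month visits follow for everyone, with photographs at each. The primary endpoint is "The time taken for patients to notice a self-determined significant difference between their right and left side and request the full garment". Under Secondary endpoints, the photograph endpoint is "Changes in photographs 0, 3, 6 months as assessed by 2 'blinded' observers". The water endpoint names no times, and Celluqol is set at 0, 3 and 6 months.

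**The concern.** From the swap onwards the former control side also receives pads. A photograph at month 3 or 6 in a woman who has already switched no longer compares a side currently padded with one currently unpadded. Her last photographs after one-sided wear are those taken at the variable visit, and the endpoint does not list that visit.

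The loss is not random. The swap is triggered by the primary event, so each primary event takes away the concurrent control in that woman's later photographs. The women affected are exactly those who perceived a difference. Their own reports are unblinded, since a woman can tell which side of her garment has pads. The blinded photograph reading is an objective check on those reports. If the second side catches up after the swap, the side difference shrinks selectively in these women, and a null photograph result could not be read as showing that the pads add nothing to compression.

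**Working it through.** **Step 1. What the schedule gives, without assumptions.** Count the listed post-baseline photograph sets (months 3 and 6) taken while one side is still unpadded. Then add the variable visit, where photographs precede the new garments in the list.

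| When the woman switches | Month 3 one-sided? | Month 6 one-sided? | Listed one-sided sets | With variable visit added |
|---|---|---|---|---|
| Before month 3 | no | no | 0 | 1 |
| Between months 3 and 6 | yes | no | 1 | 2 |
| Never | yes | yes | 2 | 2 |

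Women who never report a difference are unaffected, because month 6 is their last one-sided visit. Month 3 stays valid for later switchers. If the variable visit happens to fall on the 3- or 6-month visit, the last one-sided photographs are already in the endpoint.

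**Step 2. Inputs for an illustration.** The protocol gives 60 women (4 sizes × 15 = 60). That number is a garment quota. The protocol states no effect size, standard deviation or power, so there is no power figure to reproduce. It also gives no switch rate and no speed of catch-up. Everything below is therefore assumed.

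Suppose 15 women switch before month 3, 15 more before month 6, and 30 never.

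- One-sided at month 3: 60 − 15 = 45 women.
- One-sided at month 6: 60 − 30 = 30 women.
- Listed post-baseline sets that are one-sided: 45 + 30 = 75 of 120.
- Women with no listed one-sided post-baseline set: 15, or 0 with the variable visit added.

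**Step 3. Share of the mean side difference retained.** Let s be the share switched by the visit, c the catch-up of the second side (0 none, 1 full), and r the switchers' true difference relative to the other women's. Then

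R = 1 − c·w, with w = s·r / (s·r + 1 − s).

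For r = 1, w = s. For r = 2, s = 0.25 gives w = 0.50/1.25 = 0.40, and s = 0.50 gives w = 1.00/1.50 = 0.667.

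**Step 4. Effect on power.** Take a paired (one-sample t) test on side differences, n = 60, two-sided 5%, with 80% power at the undiluted difference. That requires a difference of 0.368 SD, which is then multiplied by R.

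| Switched by visit (s) | r | Half catch-up: R, power | Full catch-up: R, power |
|---|---|---|---|
| 5/60 | 1 | 0.96, 77% | 0.92, 73% |
| 10/60 | 1 | 0.92, 73% | 0.83, 65% |
| 15/60 | 1 | 0.875, 69% | 0.75, 56% |
| 30/60 | 1 | 0.75, 56% | 0.50, 29% |
| 15/60 | 2 | 0.80, 61% | 0.60, 39% |
| 30/60 | 2 | 0.667, 46% | 0.333, 15% |

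With c = 0, R = 1 in every row and nothing is lost. The calculation shrinks the mean and holds the SD fixed. A simulation that keeps the mixture of switched and unswitched women agrees within about 1.5 percentage points.

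**The case against.** Five points can be made for the protocol as written.

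- **Analysis detail belongs in the SAP, which is not at hand.** This holds for how the contrast is computed and tabulated. It does not hold for the endpoint times, which the protocol fixes itself. An SAP that added the variable visit would depart from the endpoint as written.
- **The endpoint speaks of changes in photographs and does not say that sides are compared.** True, but a side comparison is the only reading under which the photographs answer the trial's question. The one-sided garment exists for that purpose.
- **Fixed visits are defensible.** They avoid measuring a woman at a moment she chose because she saw or felt a difference. This stands. A contrast at the variable visit is self-timed and may be inflated if reports mostly favour the padded side. It is a reason to report both contrasts and to rest no claim on the self-timed one alone.
- **The magnitude is assumed.** This stands too. With few switchers the loss is small (first rows of the second table), and full catch-up by month 3 is an extreme for a woman swapped shortly before that visit. The counts in the first table need no such assumption.
- **Wear after the swap may vary,** since continuing with the two-sided garment is offered as an option. That affects how far the second side catches up. It does not restore a control side kept in one-sided wear.

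**Conclusion.** The concern holds. As worded, the photograph endpoint gives 0, 1 or 2 one-sided post-baseline sets for early, late and never switchers, against 1, 2 and 2 if photographs already taken at the variable visit are included. This rests on the schedule alone, with the minor exception of a variable visit that coincides with month 3 or 6.

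The effect on the result is selective and, if there is catch-up, runs towards no difference. Its size is unknown. It is nil without catch-up. Under the assumed 15 + 15 switchers with equal differences in all women, half catch-up retains 88% of the side difference at month 3 and 75% at month 6, and full catch-up retains 75% and 50%.

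The scope is narrow. The primary endpoint is not affected. The water endpoint names no times, so it excludes nothing but would be clearer if it named the visit. Celluqol never had a control side, so its 3- and 6-month scores can only be split by garment worn. This should be fixed: it concerns a secondary endpoint, but one that carries a blinded, objective check on the trial's question.

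**What to change.** The swap stays as it is. Only endpoint wording and analysis change.

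1. Define the photograph and water endpoints as the padded-minus-unpadded difference in change from baseline.
2. Add the variable end-point visit to the photograph endpoint times, and name it for water, as the last one-sided measurement in women who switch.
3. Present 3- and 6-month results, including Celluqol, by garment worn. This can be derived from the date of the variable visit. Label post-swap data as uncontrolled for the pad question.
4. Report the fixed-visit contrast in all women (possibly diluted) beside the contrast at the last one-sided visit (self-timed, possibly inflated). Rest no claim of a pad effect on the latter alone.

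The cost is a few lines of wording, assessment of photographs that are already taken, and a little more analysis. The drawback is that two estimates with opposite possible biases have to be reported and explained.

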We will be asking for volunteers of who are adult women (over the age of 18 years old), who are able to walk normally and have cellulite of their buttocks and/or upper thighs. We will ask them to check the inclusion and exclusion criteria and, if they believe that they are able to be part of the trial, they will be given an appointment to see the trial coordinator.

Inclusion Criteria:

- Women, over the age of 18 years old, who are able to walk normally and who have cellulite on their buttocks and/or upper thighs.

Due to having to produce special garments for this trial where only half of the garment has the Vari-pads, there will be for following restrictions:

Total number = 60

Volunteers will be asked their sizes (Small, Medium, Large and Extra-large) and will only be invited to attend if there are available places in that size category.

Sizes:

- Small = 15
- Medium = 15
- Large = 15
- Extra-large = 15

Exclusion Criteria:

- Women under 18 years of age.
- Women who are pregnant or who intend to get pregnant in the next 6 months.
- Women with no discernible cellulite on initial examination.
- Women undergoing any other treatment which aims to reduce the appearance of cellulite.
- Women who are unable to complete at least 3 months of this trial.

The Trial:

Volunteers will be asked to email their interest in the trial and will be asked to check that they fit the inclusion and exclusion criteria. If they do, they will be given a free of charge appointment.

Potential volunteers will then be sent the subject information sheet by email so they have ample opportunity to both read about the trials but in addition, to ask any questions before their first appointment. These can be answered by email. In this way, we hope that most volunteers will be suitable to proceed with the trial. We will stop recruitment when a maximum 60 subjects have been enrolled.

The garments will be worn for at least 8 hours per 24 hours. For hygiene reasons, we suggest that briefs/pants are worn under the garment. However, to increase the area of contact between garment and cellulite, we suggest wearing a thong, "high thigh", or similar panties.

There will be 4 visits required:

- 1] First Visit Start of trial
- 2] 3 Months Visit
- 3] 6 Months Visit End of trial

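### Does the 1-month visit named in the interim analysis, but missing from the visit schedule, call for a change to the plan?

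*Protocol*

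**What the plan says.** The Interim Analysis section is a single sentence: "We will perform an initial analysis when all of the results are in from the 1 month and 3 months visit". It gives no stopping boundary, hypothesis test or action that depends on the result.

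The visit list under The Trial is numbered and opens with "There will be 4 visits required". Its first two entries are "1] First Visit Start of trial" and "2] 3 Months Visit". The third is the 6-month visit that closes the trial, and the fourth is the variable end-point visit. On the last, the protocol adds that "if the subject does not reach this end point, they will only have 3 visits".

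Two of the three secondary endpoints have stated times: "Quality of life changes by Celluqol® questionnaire 0, 3 and 6 months" and "Changes in photographs 0, 3, 6 months as assessed by 2 'blinded' observers". The third, transcutaneous water measurement, has none. The heading of the 6 Months Visit adds "end of trial and £100 paid if all visits completed", while the Payment paragraph ties the £100 to finishing the trial to 6 months.

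**The concern.** An analysis trigger should name data that the trial collects. This one names two visits, and one of them appears nowhere else: it is not in the visit list, has no procedures and matches no endpoint time. A reader cannot tell from that sentence alone whether a visit was dropped from the schedule or the words are stray.

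If a visit had been dropped, the consequences would be practical. Nobody would know what to measure at it, the two stated visit counts would each be one short, and women might have been told of too few attendances. The heading of the 6 Months Visit makes the £100 conditional on attending every visit, so an unlisted visit could also raise a question about payment. If no visit was dropped, the sentence merely misdescribes the data behind the interim look.

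**Working it through.** There is no sample-size, power or error-rate figure to reproduce. The check has three parts: whether the rest of the protocol leaves room for a 1-month visit, whether the stray words move the analysis, and whether anything depends on it.

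**Step 1. Every place where a visit or time point is stated.**

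| Place in the protocol | Time points given | 1 month included? |
|---|---|---|
| The Trial, visit list | day zero, 3 months, 6 months, variable | no |
| Procedure lists by visit | day zero, variable, 3 months, 6 months | no |
| Secondary endpoint, quality of life | 0, 3, 6 months | no |
| Secondary endpoint, photographs | 0, 3, 6 months | no |
| Secondary endpoint, water measurement | none stated | not stated |
| Interim Analysis | 1 month, 3 months | yes |

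**Step 2. Visit counts.**

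- As listed: 3 fixed visits + 1 variable visit = 4, the stated total. Without the variable visit: 3, the stated lower count.
- With a fixed 1-month visit added: 4 + 1 = 5, or 4 without the variable visit. These disagree with the stated 4 and 3 respectively.

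So the list, the procedures, both counts and the two timed endpoints agree with one another. The interim sentence alone is out of line.

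**Step 3. Timing of the analysis.** Let T1 be the date when the last 1-month result would be in, and T3 the date when the last 3-month result is in. The trigger is the later of the two, max(T1, T3). In each woman a 1-month visit would come 3 − 1 = 2 months before her 3-month visit. With ordinary follow-up T3 is therefore the later date and max(T1, T3) = T3. If there is no 1-month visit, no 1-month results are outstanding and the trigger is again T3.

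**Step 4. The possible readings.**

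- *Stray words left in the sentence:* the trigger is T3 and nothing else changes.
- *A slip for the first visit:* day-zero results are in before any 3-month result, so the trigger is T3.
- *The variable end-point visit was meant:* this fits poorly, because that visit has no fixed time and some women may never have it.
- *A fixed visit was dropped from the schedule:* the trigger is still T3, but the schedule would be incomplete. This reading requires the visit list, the procedure lists and both counts all to be wrong in the same way.

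**Step 5. What depends on it.** The protocol attaches no stopping rule, test or decision to the initial analysis. A different reading of the trigger would change no stated final analysis. The primary endpoint, the time until a woman notices a difference and asks for the full garment, does not depend on any visit at 1 month.

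**The case for a change.** The strongest case for a change is that this sentence is all the protocol says about the interim analysis, and one of the two visits it names does not exist. A separate analysis plan could define what is analysed, but it could not supply data from a visit that the protocol does not schedule. The text is intact, so damage in conversion does not explain it. The remedy would cost a few words.

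The mismatch stands, and so does the point that the document does not say how it arose. The consequences drawn from it mostly do not:

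- It might be said that the trigger can never be met. That is too strong. The condition is that all results are in. Where no 1-month results are due, none are missing, and it is met when the 3-month results are complete.
- The payment argument arises only if a visit was dropped. Even then the Payment paragraph, which looks to completion at 6 months, leaves it unsettled whether such a visit would count.
- Rewriting the trigger to add results from variable end-point visits would go beyond reconciling the text. The protocol does not name that visit in the trigger, and it is where the primary endpoint event is reported. Naming it would be a new choice about the interim data.

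**Conclusion.** The concern is right about the wording but does not call for a change to the plan. The interim sentence names a visit that the trial does not have, most likely by a clerical slip. On the slip reading the effect is nil: 0 visits, 0 endpoints and 0 data items change, and the analysis falls when the last 3-month results are in.

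This rests on two assumptions. The first is that no 1-month visit was intended, which the visit list, the procedure lists, both visit counts and the two timed secondary endpoints support. The second is that the initial analysis carries no decision rule, as in the protocol shown. If a 1-month visit had been intended, both counts would be short by one and its procedures would be missing, but nothing outside the interim sentence points that way. The stray words can be tidied if the document is opened for another reason.
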